6.5 Estimation of CLcr (eCLcr)

CLcr will be estimated using Cockcroft-Gault formula.

$$\text{eCLcr (mL/min)} = \{[140 - \text{age (years)}] \times \text{weight (kg)} / 72 \times \text{S}_{\text{cr}} (\text{mg/dL})\} \times (0.85 \text{ if female})$$

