6.4 Estimation of GFR (eGFR)

GFR in Groups 1 to 3 will be estimated using the 3-variable Japanese equation.

3-variable Japanese equation [7]:

$$\text{eGFR (mL/min/1.73 m}^2\text{)} = 194 \times (\text{S}_{\text{cr, std}})^{-1.094} \times (\text{Age})^{-0.287} \times (0.739 \text{ if female})$$

$\text{S}_{\text{cr, std}}$: serum creatinine measured with a standardized assay (mg/mL)

The subjects will be stratified to three different groups of renal function according to their eGFR (normal and mild or moderate impairment) at Day -1. Other eGFR measurement will be performed at 24 and 48 hr after dosing and Follow-up visit.

Table 6 Classification of Renal Function Based on Estimated GFR

Group	Description	Estimated GFR (mL/min/1.73 m ²)
1	Mild renal impairment	60 - 89
2	Moderate renal impairment	30 – 59
3	Normal renal function	≥90

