6.7.4 Routine laboratory evaluations

Blood and urine samples will be collected for routine clinical laboratory safety evaluations according to Table 5. The laboratory safety evaluations performed during the study are presented in Table 7.

Additional laboratory safety evaluations will be performed at other times, if judged to be clinically appropriate, or if the ongoing review of the data suggests a more detailed assessment of laboratory safety evaluations is required.

The Investigator will perform a clinical assessment of all laboratory safety data and the recording will be reported as 'normal', 'abnormal clinically significant (CS)', or 'abnormal not clinically significant (NCS)'. Abnormalities of clinical significance will be reported as AEs. Repeat measurements will be performed if needed.

Table 7 Routine laboratory evaluations

Haematology:	
Haemoglobin	Mean corpuscular haemoglobin (MCH)
Haematocrit	Mean corpuscular haemoglobin concentration (MCHC)
Platelet count	Mean corpuscular volume (MCV)
Red blood cell (RBC) count	White blood cell (WBC) count and differential
Biochemistry:	
Alkaline phosphatase (ALP)	Uric acid
Aspartate aminotransferase (AST)	Protein (total)
Alanine aminotransferase (ALT)	Albumin
Gamma-glutamyl transpeptidase (GGT)	Cholesterol
Potassium	Triglycerides
Sodium	High density lipoprotein-cholesterol (HDL-C)
Chloride	Low density lipoprotein-cholesterol (LDL-C)
Calcium	Lactate dehydrogenase (LDH)
Inorganic phosphate	Amylase
Glucose	Creatine kinase (CK)
Blood urea nitrogen	Creatinine ^{1,2}
Bilirubin (direct and total)	Follicle stimulating hormone (FSH) ³
Coagulation:	
Prothrombin time	Activated partial thromboplastin time (aPTT)
Urinalysis:	
Specific gravity, sediment, pH, protein, glucose, ketones, urobilinogen, bilirubin, blood hCG ⁴	
Microscopic examination ⁵	
Serology:	
Hepatitis B surface antigen (HBsAg)	Human immunodeficiency virus (HIV) antigen/antibodies
Hepatitis C virus antibody (HCVAb)	
Drugs and alcohol screen:	
Phencyclidine, cocaine, barbiturates, tetrahydrocannabinol, benzodiazepines, amphetamines/methamphetamines, opiates, and alcohol breath test	

¹ eGFR will be calculated using the 3-variable Japanese equation² eCLcr will be calculated using the Cockcroft-Gault formula³ Females only; performed at Screening only⁴ Females only; a urine pregnancy test will be performed at Screening, Day -1 and follow-up⁵ Performed only if required, based on urinalysis results

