10.3.5 Analysis of secondary endpoints

10.3.5.1 Pharmacokinetic endpoints

In addition to the primary PK endpoints the following PK parameters will be determined, where possible, from the individual concentration-time data of MCI-186 and its metabolite in plasma by non-compartmental analysis methods using [REDACTED]. The actual, exact sampling times in relation to dosing will be used. For calculation of PK parameters, concentrations below the limit of quantification (BLQ) will be imputed with a value of zero.

PK parameters of MCI-186

- Half-life ($t_{1/2}$);

Individual and mean plasma concentration versus time curves will be plotted by each group (Group 1, 2 and 3) on both linear/linear and log/linear scales separately for MCI-186 and its metabolite.

Individual plasma concentration of MCI-186 and its metabolite will be listed.

Summary statistics (number of subjects [N], n, mean, SD, CV%, median, minimum, maximum, geometric mean, and geometric CV%) will be calculated for plasma concentrations of MCI-186 and its metabolite at each group (Group 1, 2 and 3). For the calculation of the summary statistics, concentration values reported as BLQ will be set to zero.

The PK parameters will be summarized. Summary statistics (N, n, mean, SD, CV%, median, minimum, maximum, geometric mean, and geometric CV%) will be presented for all PK parameters by each group (Group 1, 2 and 3).

The following graphics will be produced for the relationship between measures of renal function (on the horizontal axis) and $AUC_{0-\text{last}}$, $AUC_{0-\infty}$, [REDACTED] and C_{\max} of MCI-186 (on the vertical axis):

For each renal function group: Scatter plots of $AUC_{0-\text{last}}$, $AUC_{0-\infty}$, [REDACTED] and C_{\max} of MCI-186 versus eGRF and eCLcr with regression line.

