7.8.2 Analysis of Pharmacokinetic Parameters

All PK parameters will be listed.

The PK parameters will be summarized by each group (Groups 1, 2 and 3). The following descriptive statistics will be calculated: N (number of subjects), n (number of valid observations), arithmetic mean, SD, CV%, minimum, median, maximum, geometric mean and geometric CV%.

For the descriptive statistics, the minimum and maximum will be presented according to following requirement:

- C_{\max} : will be presented with the number of significant digits they are reported with.
- Other PK parameters: will be presented with a fixed number of decimal places for each parameter. The number of decimal places is 2 decimal places corresponding to having 3 significant digits at the minimum by analyte.

Mean, SD, median and geometric mean will be presented with the number of decimals as follows.

- C_{\max} : will be presented with 4 significant digits.
- Other PK parameters: will be presented with 2 decimal places.

CV% and geometric CV% will be presented with 1 decimal place.

To visualize the relationship between measures of renal function and between the PK parameters of MCI-186 and the sulfate conjugate, the following scatter plots of $AUC_{0-\text{last}}$, $AUC_{0-\infty}$, [REDACTED] and C_{\max} (on the vertical axis) versus eGFR and eCLcr (on the horizontal axis) with regression line, will be produced in linear scales:

1. The PK parameters of ($AUC_{0-\text{last}}$, $AUC_{0-\infty}$, [REDACTED] and C_{\max} of MCI-186 and the sulfate conjugate) vs (eGFR and eCLcr) plot will be produced for all subjects overlaid in one graph.

Regarding the log-transformed values of $AUC_{0-\text{last}}$, $AUC_{0-\infty}$ and C_{\max} of MCI-186 and the sulfate conjugate, analysis of variance (ANOVA) will be performed with groups as factors.

The estimated LSmeans and associated two-sides 95% confidence intervals for these PK parameters in each group, and the estimated LSmeans and associated two-sided 90% confidence intervals for the differences of each the renal impairment group (Group 1 or 2) compared to the normal renal function group (Group 3) will be calculated.

The calculated values will be retransformed using antilogarithms and displayed.

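### Protocol 6.5 prints the Cockcroft-Gault formula without brackets round the denominator, so eCLcr would rise with serum creatinine if the line were coded as written

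*Protocol*

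**What the plan says.** Protocol 6.5 states that "CLcr will be estimated using Cockcroft-Gault formula". It then prints the expression inline: 140 minus age, times weight, a division sign, then "72 \times \text{S}_{\text{cr}} (\text{mg/dL})\} \times (0.85 \text{ if female". One pair of braces encloses the whole expression up to the sex factor. No bracket joins 72 and Scr.

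The visible text does not write the formula out anywhere else. Footnote 2 to Table 7 (Protocol 6.7.4) says only that "eCLcr will be calculated using the Cockcroft-Gault formula". SAP 5.6 spells out age and BMI as derived variables but gives no line for eCLcr.

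eCLcr is used in two visible analyses. SAP 7.2 lists it as a Day -1 baseline variable. Protocol 10.3.5.1 plots exposure "of MCI-186 versus eGRF and eCLcr with regression line", and SAP 7.8.2 repeats those plots for MCI-186 and the sulfate conjugate, with the PK parameters "on the vertical axis) versus eGFR and eCLcr (on the horizontal axis) with regression line, will be produced in linear scales".

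Grouping rests on the other measure. Protocol 6.4 says: "The subjects will be stratified to three different groups of renal function according to their eGFR".

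**The concern.** Clearance has to fall as creatinine rises. The eGFR equation in Protocol 6.4 does this through its negative exponent on creatinine. The line in 6.5, evaluated strictly, does the opposite. It is the only written specification of eCLcr, so a programmer who works from the page has nothing to correct it against. The double programming in SAP section 11 would not expose the error if both programmers coded the same line.

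The eCLcr plots are half of the renal-function plots, and the plots are the only visible analysis that treats renal function as continuous. Coded literally, the eCLcr regression lines would slope against the eGFR lines. SAP 5.3 also sets reporting digits for α, β and Spearman's ρ. If those are the statistics for these plots, which the SAP does not say, the sign of reported numbers could be affected as well.

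**Working it through.** The documents state no eCLcr value, so there is no figure of the plan's own to reproduce. The check compares the two readings of the printed line.

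**Inputs.** The eCLcr expression is from Protocol 6.5. The eGFR equation is from Protocol 6.4: 194 × Scr^-1.094 × age^-0.287 (× 0.739 if female). Scr is taken in mg/dL, as in 6.5; section 6.4 prints mg/mL, a separate discrepancy to reconcile. Age, weight and sex are assumptions.

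**Formulas (male)**
- As printed, left to right: (140 − age) × weight / 72 × Scr
- Bracketed: (140 − age) × weight / (72 × Scr)
- Ratio of printed to bracketed: Scr × Scr = Scr². The two agree only at Scr = 1.0 mg/dL.

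**Man of 65 years, 65 kg.** (140 − 65) × 65 / 72 = 4875 / 72 = 67.71.

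| Scr (mg/dL) | eGFR (6.4) | eCLcr bracketed | eCLcr as printed |
|---|---|---|---|
| 0.65 | 93.8 (Group 3) | 67.71 / 0.65 = 104.2 | 67.71 × 0.65 = 44.0 |
| 0.85 | 69.9 (Group 1) | 67.71 / 0.85 = 79.7 | 67.71 × 0.85 = 57.6 |
| 1.30 | 43.9 (Group 2) | 67.71 / 1.30 = 52.1 | 67.71 × 1.30 = 88.0 |

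The bracketed form keeps the order of the groups. The printed form reverses it.

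**Other profiles, all 60 kg.** Scr is found by inverting the eGFR equation and is not rounded before use.

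| Profile | Bracketed, eGFR 90 → 30 | As printed, eGFR 90 → 30 |
|---|---|---|
| Male, 40 y | 108.7 → 39.8 | 63.9 → 174.4 |
| Male, 60 y | 96.7 → 35.4 | 46.0 → 125.4 |
| Male, 70 y | 88.1 → 32.3 | 38.6 → 105.4 |
| Female, 60 y | 108.4 → 39.7 | 29.6 → 80.9 |

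For the 60-year-old man, Scr² is 0.48 at eGFR 90 and 3.54 at eGFR 30. The direction is the same in every profile.

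**Illustrative simulation.** I took 2,000 samples of 11, 8 and 11 subjects, with eGFR uniform within each group (60–89.9, 30–59.9 and 90–110), age 50–75 years, weight 50–75 kg and mixed sex. The mean Spearman correlation of eCLcr with eGFR was −0.71 for the printed form (2.5th to 97.5th percentile −0.85 to −0.52). For the bracketed form it was +0.87 (0.78 to 0.94).

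**The case against.** The best reply is that this is loose notation. The protocol names the method twice, and an inline a / b × c is common shorthand for division by the product. A competent programmer would probably code the known method. A clearance that ran against eGFR in the companion plots would also be conspicuous. This stands: the harm is conditional on literal coding.

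A flattened stacked fraction is also possible, because the text was extracted from PDF. The slash and outer braces point to inline typesetting, as does the BMI formula in Protocol 6.7.1, and stacked fractions survive in SAP 7.8.1 and Appendix 1. Those surviving fractions are in the other document, however, so the original page should be checked.

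A reader might infer more than the documents support, in three ways:
- **That the renal-function axis is reversed.** There are two axes, and the eGFR axis is untouched. No eCLcr value is shown, so nothing shows that any calculation has gone wrong.
- **That the primary comparison is affected.** Groups and inclusion criteria 7 and 10 use eGFR. The ANOVA in SAP 7.8.2 has group as its only factor, and SAP 7.7.1 rules out covariate adjustment.
- **That a post-dose rise in creatinine would pass as improving clearance.** Protocol 5.2.2.2 and 5.2.3 do recalculate eCLcr after dosing, but no visible SAP table names post-dose eCLcr. Creatinine is itself a biochemistry test, summarised with change from baseline (SAP 7.9.2), and the criterion in Protocol 4.5 for progressing to Group 2 uses creatinine directly. A rise would be seen as creatinine.

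**Conclusion.** The defect holds as a notation error in an operative section. Under standard operator order the printed line contradicts the method it names, and no other visible text corrects it. If coded literally, eCLcr would be wrong by a factor of Scr²: about half the intended value at eGFR 90 and about 3.5 times it at eGFR 30, for a man of 60 years. The size depends on the assumed age and sex, since these set the creatinine at a given eGFR; the direction was the same in all profiles tried.

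The reach is limited to the Day -1 eCLcr summary and the eCLcr scatter plots with their regression lines. The conclusion assumes that the extracted line matches the original page. Severity is minor.

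**What to change.** Check the original page of Protocol 6.5. If it matches the extracted text, write:

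eCLcr (mL/min) = {[140 − age (years)] × weight (kg)} / {72 × Scr (mg/dL)} × (0.85 if female)

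The protocol does not print this bracketed form. It follows from the named method, and its direction agrees with the inverse relation to creatinine in 6.4.

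Before the analysis, confirm that the programmed or laboratory-reported eCLcr values use this form. One check value is enough: male, 65 years, 65 kg, Scr 1.3 mg/dL gives 52.1 mL/min, where literal coding gives 88.0. Repeating the formula in SAP 5.6 would be good practice but is optional.

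The cost is one corrected line and a short code check. No new data are needed, and the design and primary analysis do not change.

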6.6 Pharmacokinetic assessments

6.6.1 Collection of blood samples for PK analysis of MCI-186 and its metabolite

A series of 12 horizontal black bars of varying lengths, decreasing from left to right. The bars are evenly spaced and have a consistent thickness. The lengths of the bars decrease in a regular, stepped pattern from the first bar on the left to the last bar on the right.

6.7 Safety assessments

Please refer to Section 8 for details of AE management.
The results of safety assessments will be recorded in the CRFs

6.7.1 Physical examination

At the times indicated in the Time and events schedule (Table 5), subjects will undergo a routine assessment of major body systems (general appearance, cardiovascular, neurological, respiratory, head, eyes, ear/nose/throat, lymph nodes, abdominal, hepatic, gastrointestinal, musculoskeletal, neck, dermatological, and 'other').

Body weight will be measured at the times indicated in the Time and events schedule (Table 5). Height will be measured once only (at Screening). The BMI will be calculated using the standard formula at Screening.

Body mass index calculation:

$$\text{BMI} = \text{Weight [kg]} / (\text{Height [m]})^2$$

6.7.2 Vital signs

At the times indicated in the Time and Events Schedule (Table 5), subjects will undergo an assessment of systolic blood pressure (SBP) and diastolic blood pressure (DBP) using an

automatic blood pressure measurement device with an appropriate cuff size after the subject has rested for at least 5 minutes in a supine position. 3 repeated measurements will be performed and a mean of the measurements will be calculated. The same arm will be used for all measurements. Pulse rate (beat/min) and infra-axillary body temperature will also be measured.

The Investigator will perform an overall evaluation for safety purposes and the recording will be reported as 'normal', 'abnormal clinically significant (CS)', or 'abnormal not clinically significant (NCS)'. Abnormalities of clinical significance will be reported as AEs. Repeat measurements will be performed if needed.

6.7.3 Electrocardiogram

At the times indicated in the Time and Events Schedule (Table 5), a 12-lead ECG will be performed after the subject has rested for at least 5 minutes in the supine position.

The following ECG parameters will be recorded: heart rate, RR-interval, PR-interval, QRS duration, QT-interval and QTc. The QTc-interval will be calculated automatically according to Fridericia's formula. In case of results >450 ms in healthy subjects or renal impairment subjects, repeat measurements will be performed.

The Investigator will perform an overall evaluation of the ECG for safety purposes and the recording will be reported as 'normal', 'abnormal clinically significant (CS)', or 'abnormal not clinically significant (NCS)'. Abnormalities of clinical significance will be reported as AEs. Repeat measurements will be performed if needed.

6.7.4 Routine laboratory evaluations

Blood and urine samples will be collected for routine clinical laboratory safety evaluations according to Table 5. The laboratory safety evaluations performed during the study are presented in Table 7.

Additional laboratory safety evaluations will be performed at other times, if judged to be clinically appropriate, or if the ongoing review of the data suggests a more detailed assessment of laboratory safety evaluations is required.

The Investigator will perform a clinical assessment of all laboratory safety data and the recording will be reported as 'normal', 'abnormal clinically significant (CS)', or 'abnormal not clinically significant (NCS)'. Abnormalities of clinical significance will be reported as AEs. Repeat measurements will be performed if needed.

Table 7 Routine laboratory evaluations

Haematology:	
Haemoglobin	Mean corpuscular haemoglobin (MCH)
Haematocrit	Mean corpuscular haemoglobin concentration (MCHC)
Platelet count	Mean corpuscular volume (MCV)
Red blood cell (RBC) count	White blood cell (WBC) count and differential
Biochemistry:	
Alkaline phosphatase (ALP)	Uric acid
Aspartate aminotransferase (AST)	Protein (total)
Alanine aminotransferase (ALT)	Albumin
Gamma-glutamyl transpeptidase (GGT)	Cholesterol
Potassium	Triglycerides
Sodium	High density lipoprotein-cholesterol (HDL-C)
Chloride	Low density lipoprotein-cholesterol (LDL-C)
Calcium	Lactate dehydrogenase (LDH)
Inorganic phosphate	Amylase
Glucose	Creatine kinase (CK)
Blood urea nitrogen	Creatinine ^{1,2}
Bilirubin (direct and total)	Follicle stimulating hormone (FSH) ³
Coagulation:	
Prothrombin time	Activated partial thromboplastin time (aPTT)
Urinalysis:	
Specific gravity, sediment, pH, protein, glucose, ketones, urobilinogen, bilirubin, blood hCG ⁴	
Microscopic examination ⁵	
Serology:	
Hepatitis B surface antigen (HBsAg)	Human immunodeficiency virus (HIV) antigen/antibodies
Hepatitis C virus antibody (HCVAb)	
Drugs and alcohol screen:	
Phencyclidine, cocaine, barbiturates, tetrahydrocannabinol, benzodiazepines, amphetamines/methamphetamines, opiates, and alcohol breath test	

¹ eGFR will be calculated using the 3-variable Japanese equation² eCLcr will be calculated using the Cockcroft-Gault formula³ Females only; performed at Screening only⁴ Females only; a urine pregnancy test will be performed at Screening, Day -1 and follow-up⁵ Performed only if required, based on urinalysis results

Blood and urine samples will be analysed by [REDACTED] using standard methods. Laboratory safety measurements will be performed according to [REDACTED] SOPs. Procedures for the handling of samples will be described in full in a separate document.

6.8 Total blood volume

The approximate total blood volume taken per subject is given in Table 8.

Table 8 **Blood volumes**

Additional or repeat safety laboratory samples may be taken during the study if required by the Investigator. The volume to be drawn from each subject will be approximately [REDACTED].

7 STUDY TREATMENT

7.1 Investigational Medicinal Product

A description of the IMP is given in Table 9.

Table 9 Investigational Medicinal Product

	MCI-186 injection
Dosage form	Aqueous solution for injection
Description	Clear and colorless
Strength	30 mg of edaravone per 20 mL ampule
In active excipients (per 20 mL ampule)	Sodium bisulfite: 20 mg L-cysteine hydrochloride hydrate 10 mg Sodium chloride: 135 mg Sodium hydroxide: q.s. Phosphoric acid: q.s.
Storage conditions	Room temperature

IMP (MCI-186 injection) will be manufactured by the Sponsor. Commercially available drug product, RADICUT® inj. 30 mg manufactured by [REDACTED], is overlabelled.

Ten overlabelled ampules will be packed in a paper carton and certified by the Sponsor.

IMP is tested and released according to Good Manufacturing Practice.

IMP will be labeled with the Sponsor's name and address, chemical name or identification code, and storage conditions. The label will contain the statement: "Investigational Product: to be used in a clinical investigation only" or other similar statement. All labelling will comply with applicable regulatory requirements.

7.1.1 Compliance

IMP will be administered by the Investigator or designee. The prescribed dosage, timing and mode of administration of study medication may not be changed. Any departures from the intended regimen must be recorded in the CRF.

IMP accountability and subject compliance will be documented throughout the study period using study-specific IMP dispensing. The Investigator, or suitably qualified staff member, will supervise/oversee the administration of IMP and the exact time of dosing will be recorded in the CRF.

7.1.2 Shipping, receipt, handling and storage

IMP will be shipped from [REDACTED] to the clinic in a temperature-controlled shipping system after completion of a clinical contract between the Sponsor and study center.

On receiving a shipment of the IMP at the study center, the designee will conduct an inventory check and complete a supplies receipt document, and the receipt will be returned to the Sponsor. The designee will maintain a record of all IMPs received and returned.

At the study center, IMP will be stored at room temperature in a locked, restricted access area. The temperature will be recorded throughout the study and a daily minimum and maximum temperature log will be maintained. A temperature log recording will be

maintained daily throughout the course of the study. Any temperature deviations will be reported to the Sponsor.

7.1.3 Dispensing

The treatments will be dispensed by the Investigator or designee. A record of the IMP dispensed to each subject will be maintained by the designee in an Accountability Log. Any opened ampule will not be redispensed.

Investigator or designee will dilute one ampule (30 mg of MCI-186) with 100 mL of physiological saline. All subjects will be administered intravenous infusion 30 mg of MCI-186 over 60 minutes in the morning of Day 1 by the Investigator or designee. Detailed procedure is described in a separate document.

